Subjects with more medial ankle fractures, in whom some of the affected region may lie outside of the popliteal distribution, will be eligible for the study. As part of standard care, such patients generally receive either a second single shot nerve block (saphenous) or rely on opioid anesthesia, depending on the preference of the anesthesiologist. Such patients will still receive only a popliteal continuous nerve block after the surgery. Since preclinical and clinical studies indicate that chronic pain rarely develops in purely sensory nerves such as the saphenous, we consider it consistent with the primary hypothesis to include such patients. The characterization of the fracture will be included in the clinical information captured by the study.

The infusion pumps and 800 mL bags of ropivacaine will be provided by the UC Health Investigational Pharmacy at the University of Cincinnati Medical Center. The ropivacaine 0.2% 800 mL bags will be compounded by certified pharmacy technicians and registered pharmacists in a certified ISO Class 5 biologic safety cabinet within an ISO Class 7 buffer room at the University of Cincinnati Medical Center consistent with USP 797 standards and American Society of Health-System Pharmacists (ASHP) guidelines [20]. The bags will be prepared by combining four, sterile, preservative-free, commercially available ropivacaine 0.2% 200 mL bags/bottles[21] (stable at controlled room temperature up to manufacturer's expiration date) into a 1,000 mL empty sterile bag (e.g., Baxter Viaflex bag) using a single sterile fluid transfer set. Using aseptic technique, the

infusion spike of the sterile fluid transfer set will be inserted into each commercial bag/bottle to drain completely (including any overfill) into the empty sterile bag via single needle manipulation of the injection port. After the fourth bag/bottle is drained, the needle and transfer set will be disconnected from the compounded bag, and the injection port will be aseptically covered with a foil seal. A total of 4 to 8 ropivacaine 800 mL bags will be batched at a time. Compounded ropivacaine 0.2% 800 mL bags will be dispensed by the inpatient investigational pharmacy following a patient-specific order from a research provider.

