There are no additives in the final ropivacaine 800 mL bag that would affect stability beyond that of the commercial product. In order to ensure the sterility of the ropivacaine during the 5 days of use, the following procedure will be used: The final ropivacaine 800 mL bags will be considered medium-risk compounded sterile products (CSP). In lieu of a separate sterility test, USP 797 guidance indicates medium-risk CSPs should have a beyond use date (BUD) of 30 hours when stored at room temperature. To extend the BUD, sterility testing will be performed on each batch of ropivacaine 800 mL bags. Two of the bags in each batch will be tested for sterility using the QT JuniorTM System (Q.I. Medical, Inc., Grass Valley, CA, USA), which utilizes a 0.22-micron filtration set and fluid thioglycollate growth media [22]. The batched bags will remain quarantined before use for 14 days after preparation. On day 14, the QT systems being incubated from the 2 tested bags will be visually inspected for turbidity per the manufacturer instructions. If no turbidity is seen (i.e., negative growth) at day 14, then the batched bags will be released for dispensing for an additional 14 days (i.e., 28 days total from preparation: 14 days quarantined plus 14 days post-release) while being stored at controlled room temperature in the investigational pharmacy until dispensed or expired. Released bags will only be dispensed if the BUD does not extend beyond the planned 5-day therapy for a specific patient. Following the patient-specific dispense, the ropivacaine bag and pump will be connected directly to the nerve block catheter at the time the catheter is inserted, in the same day surgery area immediately after the single popliteal nerve block is administered. The catheter will be infused using a commercially available ambulatory infusion pump consistent with standard clinical care. Infusion will begin immediately after the surgery, when the patient is in the PACU.

Subjects will be contacted by phone each day by the study nurse or other clinical study member. The script to be used for this follow-up is provided in a separate document. This allows monitoring for post-operative analgesic use, toxicity, infection, or other problems related to the use of the pump, and for reminders about when and how to remove the catheter.

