Randomization: We will use a block-stratified randomization schedule with blocks of sizes 2 and 4. The West Chester and Uptown locations will have separate randomization schedules as it is thought the two locations provide somewhat different populations, making it desirable to have approximately equal numbers in the control and experimental groups at each site. Due to the requirement for quarantine of the ropivacaine prepared by IDS, subject randomization may sometimes deviate from the schedule: a subject scheduled to receive a pump may be placed in the control group if no ropivacaine is available at the time of their surgery, which will be compensated by placing a subsequent subject scheduled to be in the control group into the experimental group when drug is available. These deviations will not be based on subject characteristics, so that assignments remain random, and the total number of control and experimental subjects at each site will remain the same.

Data collection: We will establish an online copy of the SEFAS which subjects can use to enter their responses. This will be done using the REDCap (Research Electronic Data Capture) system for secure web based capture of questionnaire data. For patients opting to have a link to the SEFAS sent to their cell phones, the REDCap-Twillio integration platform will be used. Patients electing not to use the online entry format will be contacted by the research nurse via the preferred route indicated on the consent form, and the research nurse will then enter the data into the Redcap project database. Data from the questionnaires will be exported out of REDCap to be merged with the data from the Medidata Rave® database for analysis. All other data will be entered directly into the Medidata Rave® clinical database. Clinical demographic data will be obtained from the patient at the beginning of the study and verified with the electronic medical record. Analgesic use in the perioperative period will be obtained from the electronic medical chart. Patients typically receive acetaminophen and celecoxib preoperatively, then opioids postoperatively as needed. However, participating in the study will not affect the subjects' options for treatment for pain. Numerical pain ratings recorded in the PACU will be obtained from the electronic medical chart. The Verbal Numerical Scale (VNRS, 0 = no pain, 5 = moderate pain, 10 = worst possible pain) is used for patients in the

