 A single serious adverse event of LAST requiring rescue medication, cardiac resuscitation, or transfer to the ICU.

During the 5 day period of ambulatory pump use:

 A single serious adverse event of catheter site infection requiring hospital admission.

 A single serious adverse event of LAST requiring hospital admission.

During the entire study period:

 A single serious adverse event of any life-threatening adverse event deemed possibly related to the use of the ropivacaine pump.

 Two subjects receiving pumps experiencing moderate adverse events of tinnitus and/or metallic taste in the mouth.

11. Data Safety monitoring plan and/or DSMB:

As discussed in section 6, the medical monitor, [name], will review subject's research data and adverse events to ensure patient safety.”

12. Data Analysis:

The primary outcome measure is SEFAS scores at the indicated time points. A secondary outcome measure is use of opioids in the immediate postoperative period.

Each SEFAS response has 5 ordinal response choices scored 0 through 4, with the lowest score (0) representing the most severe disability and the highest total score being 48. If subjects omit a question the score will be re-normalized; however, the Redcap interface will be designed to try to obtain an answer for each question. The Mann-Whitney test will be used to examine differences in the SEFAS scores at each time point. For analysis of SEFAS scores, the pilot study sample size of 20 per group is sufficient for detecting a difference in scores between groups of 9 points with a power of 0.8 and $\alpha = 0.05$ (using the standard deviation obtained from SEFAS use in an ankle surgery study[35]); this score would represent moving up one rank in 3/4 of the questions which would be a functionally meaningful improvement given the 0 – 4 ordinal scale employed. . Patients who are withdrawn from the study due to failure of the initial nerve block (see above) will be considered as screening failures; no follow-up data or questionnaire scores will be obtained. We consider that such a failure is unlikely to have any relationship to the chronic pain outcome we are studying. The same approach will be taken for patients who decide to withdraw from the study, or are withdrawn by the attending surgeon or anesthesiologist, after randomization but before the single shot nerve block procedure.

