A typical schedule for the potential subjects is for them to be admitted to the emergency department, diagnosed with ankle fracture, then either admitted to the hospital or sent home, after being scheduled for surgery for open reduction and internal fixation of the fracture the next day. In order to identify potential subjects, the study coordinator or others listed on the IRB protocol who have Epic privileges will review the orthopedic surgery schedules at the participating hospitals to identify potential subjects. We have applied for an IRB waiver to do a preliminary research screening in the medical record to avoid approaching potential subjects outside the age range or with polytrauma or other excluded conditions. A paper prescreening form will be used, listing inclusion and exclusion criteria, to determine as far as possible from the medical chart of scheduled patients whether the patient is eligible. If the patient agrees to join the study, this document will be kept with the consent form; if not, the document will be used to document the reason for the screening failure or to note that the patient refused to participate. The form will then be shredded; the sex, age in years, and reason for not enrolling in the study will be the only data retained. The orthopedic surgeon and the anesthesiologist scheduled to conduct the surgery will be contacted to confirm that they are willing to have the patient enrolled in the study, before subjects are enrolled. We will introduce the study to both the Anesthesiology and Orthopedic Surgery departments prior to the beginning of the study. Patients who have passed the prescreening and who will come to the surgery after hospital admission will be contacted in their rooms to invite them to participate, prior to the scheduled surgery (but after patients have been admitted to the hospital from the emergency room if that is where they initially presented). Patients who are scheduled to come to the surgery from home will be contacted at home by telephone, if they have passed the prescreening. In both cases patients will be requested to arrive at least 30 minutes earlier than otherwise scheduled so that consent and enrollment can be done in the pre-operative period. Consent will be obtained before the anesthesiologist starts the standard-of-care nerve block procedure.

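### Drug stock may override the randomisation list, so swapped assignments are not random as the protocol says, and the SAP does not settle the arm in which a swapped subject is analysed

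*Protocol*

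**What the plan says.** Protocol section 7 (Randomization) sets permuted blocks of 2 and 4, with separate lists for the West Chester and Uptown locations. It then allows an exception for supply: "a subject scheduled to receive a pump may be placed in the control group if no ropivacaine is available". A later subject listed for control takes the pump in exchange once drug is available. The paragraph draws two conclusions. The first is "These deviations will not be based on subject characteristics, so that assignments remain random". The second concerns the balance between arms, and promises that "the total number of control and experimental subjects at each site will remain the same". It does not say which later subject repays, who decides, by when, or what happens if a swap is still owed when enrolment closes.

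Protocol section 6 gives the cause of the shortage. "A total of 4 to 8 ropivacaine 800 mL bags will be batched at a time", "Two of the bags in each batch will be tested for sterility", and the life of a batch is "14 days quarantined plus 14 days post-release". No batching interval or expected availability is stated. Treatment is open label (section 6). Section 15 says that the operating surgeon and the anesthesiologist "will be contacted to confirm that they are willing to have the patient enrolled in the study, before subjects are enrolled".

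The SAP does not mention swaps. Section B words the aims by who received a pump. Section D1 names intent-to-treat only for early pump removal. Section E lists one arm variable, the group randomized to, and no field for scheduled arm, drug availability or an owed swap.

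**The concern.** Random allocation needs each assignment to be a chance event that recruiters cannot foresee. Ignoring subject characteristics when making a swap meets neither condition. Drug stock decides the arm on no-drug days, and the outstanding swap decides it afterwards. Anyone who knows the stock can foresee control on a no-drug day. Anyone who also knows that a swap is owed at a site can foresee pump, if the next control-scheduled subject repays.

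The point where this knowledge could act is before enrolment, when clinicians are asked to agree to each subject. If subjects enrolled on no-drug days differ in prognosis, that difference enters the arm contrast on an unblinded self-report, the SEFAS. The documents do not say who knows the stock. Section 6 has a research provider place a patient-specific drug order, so knowledge among study staff is plausible but not established.

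The analysis gap exists whether or not any bias occurs: a swapped subject has two candidate arms, and the SAP does not choose between them.

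**Working it through.** **The plan's own figure.** Protocol section 12 gives 20 per group for 9 SEFAS points, power 0.8, alpha 0.05, with the SD cited but not stated. Solving for the SD gives 9.9 (two-sided t-test) or 10.2 (normal approximation). The figure is consistent with an SD near 10 but cannot be reproduced independently. I use 9.9 below.

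**The rule as written.**
- No drug: P(control) = 1, whatever the list says.
- Drug in stock, swap owed, next control-scheduled subject repays: a list-pump subject gets a pump and a list-control subject is switched to one, so P(pump) = 1 at that site until repayment.
- Drug in stock, swap owed, some other subject repays: someone chooses which one.
- Only with drug in stock and nothing owed does the list decide.

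**How often.** Inputs from the protocol: two sites, blocks of 2 and 4, up to 60 enrolled. Assumed: availability, and that the next control-scheduled subject repays. The 64% case is one batch every 14 days with a 9-day dispensing window (28 − 14 − 5 = 9; 9/14 = 0.643), which reads section 6 as requiring the 5-day infusion to end by day 28. Simulation, 60 subjects:

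| Assumed availability | 95% | 90% | 75% | 64% |
|---|---|---|---|---|
| Arm fixed by stock or owed swap | 8% | 17% | 43% | 62% |
| Arm differs from list | 5% | 10% | 24% | 34% |
| At least one swap unpaid at close | 8% | 15% | 45% | 71% |
| Mean unpaid swaps, of 60 subjects | 0.07 | 0.17 | 0.63 | 1.4 |

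Hand check of the second row: if D pump subjects are displaced and U swaps stay unpaid, off-list subjects number 2D − U. At 90%, D = 0.5 × 0.10 × 60 = 3, so (6 − 0.17)/60 = 0.097.

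**Site totals.** One-for-one repayment preserves them exactly unless a swap is unpaid at close. Each unpaid swap moves one subject between arms. With 40 subjects, power is 0.80 at 20/20 and 0.784 even at 16/24.

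**Type I error.** 40 subjects, t-test by assigned arm. The prognosis gap is assumed: no-drug enrolments are worse by the stated amount. Ranges show simulation error between runs.

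| Assumed availability | 90% | 75% | 64% |
|---|---|---|---|
| No gap | 0.05 | 0.05 | 0.05 |
| 0.25 SD gap | 0.05 | 0.06–0.07 | 0.08 |
| 0.5 SD gap | 0.05–0.06 | 0.11–0.12 | 0.17–0.18 |
| Mean bias, 0.5 SD gap (SD units) | 0.10 | 0.24 | 0.33 |
| Same × 9.9 (SEFAS points) | 1.0 | 2.4 | 3.3 |

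The bias favours the pump because of the direction assumed; the opposite gap reverses it. The planned effect is 9 points.

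**Would the planned checks find it?** If the whole 0.5 SD gap lay in one measured baseline variable, the SAP's baseline comparison would flag it in about 6/11/18% of trials at 90/75/64% availability. It cannot reach unmeasured prognosis.

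**What extra analyses recover.** With the 0.5 SD gap, type I error is about 0.05 both by scheduled arm and after excluding subjects enrolled on no-drug days or while a swap was owed. The price is power:
- By scheduled arm, the contrast is 9 × (1 − 2s), with s = 0.097/0.240/0.338: 7.3/4.7/2.9 points, power 0.62/0.31/0.15.
- The exclusion analysis keeps about 33/23/16 of 40 subjects, power 0.72/0.55/0.40.

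**The case against.** The strongest defence is that this is a disclosed supply constraint in a small pilot. Swaps are said to occur only sometimes, are not tied to the patient, and are repaid one for one. Much of that stands. Without selective enrolment the test keeps its size, and at 90% availability the inflation is slight even with selection. Frequent batching could make the issue vanish: a batch every 9 days with 4 usable bags leaves about 0.8% of enrolments on no-drug days, under an assumed 60 subjects in 182 days.

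The allocation is also partly predictable already. If block boundaries were known, about (1 + 4/3)/(2 + 4) = 39% of list assignments would follow from earlier ones with an equal mix of block sizes. The share fixed by stock is therefore not an increase from zero. But list prediction requires tracking each site's blocks, whereas a no-drug day requires only knowing the stock.

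Three stronger readings are tempting, and the documents do not support them:
- That the promise on site totals is simply false. Repayment keeps totals equal unless a swap is outstanding at close, and the shortfall hardly matters.
- That dropping subjects "withdrawn by the attending surgeon or anesthesiologist, after randomization but before the single shot nerve block procedure" (Protocol section 12; SAP D1) is a second route by which stock knowledge acts. The arm can be known by then in an open-label trial, so that provision raises the same question with or without swaps.
- That stock-outs must be common. With only 2 usable bags per 9-day batch, about 24% of enrolments would meet no drug. That takes the smallest permitted batch and assumes that tested bags cannot be dispensed, which the protocol does not say; it belongs beside the 0.8% result above.

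**Conclusion.** The statement that assignments remain random is wrong as written, and this needs no assumption about supply. Equal site totals are expected but not guaranteed, with negligible effect on power. The SAP leaves the analysis arm of a swapped subject undefined.

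Bias is possible but not shown. Its size depends on three things outside the documents: drug availability, who knows the stock and owed swaps, and whether enrolment responds to that knowledge. Under the assumptions above, the effect is negligible if stock is nearly always available and small at 90% availability. It is material only at about 75% or lower with selective enrolment: type I error about 0.11 to 0.18 and bias of 2.4 to 3.3 SEFAS points for a 0.5 SD gap. A reader might infer that the trial's result is biased; the documents do not support that. The point should be fixed, because the correction is cheap and the results are meant to guide a larger trial.

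**What to change.** 1. Protocol section 7: delete the conclusion that assignments remain random, and say that site totals are expected, not guaranteed, to match the schedule. Cost: one sentence.
2. If swaps are kept, fix in advance that the next control-scheduled subject at that site repays, and keep stock and owed-swap status from those who recruit or approve enrolment. The rule removes choice but makes the arm certain while a swap is owed, so it is sound only with that concealment. Cost: one rule and a restricted log.
3. An option for subjects not yet enrolled: confirm a dispensable bag before consent and randomisation, then follow the list without swaps. This has a real accrual cost. At 90/75/64% availability, 60 candidates become about 54/45/39 (60 × availability). If 12-month follow-up must fit in the 18 months of data collection, 6 months of accrual become about 6.7/8.0/9.3 (6 ÷ availability).
4. SAP section E: record scheduled arm, assigned arm, drug availability at enrolment, and whether a swap was owed at that site. A swap flag alone is not enough, because list-controls enrolled on no-drug days (about 5/13/18% of subjects at 90/75/64%) have matching arms. State which arm the existing arm variable and intent-to-treat refer to. Cost: three extra variables and one definition.
5. SAP section D1: report 12-month SEFAS by scheduled and by assigned arm, with a sensitivity analysis excluding subjects enrolled on no-drug days or while a swap was owed. State the dilution, the reduced size and the power. These analyses are checks on the result, not a cure.

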In the experimental group, in addition to the standard single shot nerve block, subjects will receive a catheter to deliver continuous 5 day popliteal sciatic nerve block using a disposable ambulatory pain pump. The catheter will be inserted starting just prior to surgery. This procedure is readily added on to the procedure for single injection, which involves ultrasound (and in some cases nerve stimulation) guidance for insertion of a needle near the sciatic nerve at the popliteal fossa. As part of standard care for administering a peripheral nerve block, sedatives are administered on as needed basis. Typically the patient will receive midazolam 1 mg every 5 minutes as needed. The catheter is inserted

just after the nerve block injection, during the same procedure and using the same needle placement. If there is a major vascular injury during the catheter placement (placement of the peripheral nerve catheter into the artery as confirmed by withdrawal of blood from the catheter itself), the catheter will be withdrawn and the subject will not receive a pump. An ambIT portable pump (as currently used in the participating hospitals after some other types of surgeries) will be attached to the catheter at the time the block is placed, and continuous block with 0.2% ropivacaine will begin immediately after surgery. The drug delivery rate will be 6 mL/hour. An 800 mL bag of medication will be provided to the subjects to allow medication for a 5 day period without requiring the subject to return to the clinic for refill. This drug delivery rate is on the lower end of the range commonly used in our hospitals for patients taking home pumps after other types of surgeries, which are usually started at 8 mL/hour with the option of patient controlled boluses. Previous clinical studies examined infusion rates of 6 to 14 mL/hour. The lower, fixed rate was chosen for this study to help avoid toxicity, since the duration of the pump is longer than commonly used at our hospitals. The goal based on preclinical studies is to block abnormal spontaneous activity from the sensory nerves, which requires a lower dose than complete sensory block. The selected infusion rate should also avoid motor block. The daily dose will be 384 mg; the FDA data sheet [19] indicates that a cumulative dose of up to 770 mg over 24 hours is well tolerated and studies indicate that the peak systemic levels during prolonged infusion occur after approximately 3 days[12].

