Clinical trial monitoring will be conducted to ensure that the rights and well-being of human subjects are protected, to verify that the reported clinical trial data are accurate, complete and verifiable from source documents and to verify that the conduct of the trial is in compliance with the currently approved protocol/amendment(s), with Good Clinical Practices and with the applicable regulatory requirements.

Safety criteria for removing a subject from the study in the period before the end of the 5-day ambulatory pump use:

Prior to and during the popliteal nerve block and catheter placement: Subjects with a failed peripheral nerve block will not have a catheter placed and will not be included in the study (see Exclusions, below). Subjects will be discontinued and the catheter removed if there is inadequate view of the popliteal nerve under ultrasound guidance, paresthesias that do not resolve before the local anesthetic from the nerve injection takes effect, blood is present in the catheter during insertion indicating possible vascular injury, or one or more signs of local anesthetic systemic toxicity (LAST) (ringing in ears, metallic taste in mouth, lightheadedness, seizure, or cardiac compromise).

During Surgical Procedure and General Anesthetic – Subjects will be discontinued if there are one or more signs of LAST (listed above) or the catheter is inadvertently removed during the operation.

During immediate postoperative period in PACU – Subject will be removed if there are one or more signs of LAST (listed above) or if the catheter is removed inadvertently

After Discharge for period the pump is used: Based on the daily phone contacts, subjects will stop using the pump if there are, signs of local infection(after evaluation by the Acute Pain Service; subject would be called back into the hospital), or one or more signs of LAST (listed above). Subjects who experience paresthesias that cause them discomfort, or weakness that prevents them from participating in physical or occupational therapy, will be asked to return to the clinic for evaluation by an anesthesiologist. If these issues cannot be resolved (e.g. by lowering the dose), these subjects will have the catheter and pump removed. Subjects who must remove the pump early for any reason will be retained in the study for purposes of answering the pain surveys.

Defining and Reporting of Adverse Events:

Adverse event Definitions:

Adverse Event

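### Protocol section 10 removes pump-arm subjects from the study for catheter events after randomisation, and once infusion has started in the PACU this conflicts with the intent-to-treat rule (minor)

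*Protocol*

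**What the plan says.** Consent and randomisation take place before surgery, and only experimental subjects receive a catheter (Protocol section 7, Encounters). Section 10 then gives rules under the heading "Safety criteria for removing a subject from the study in the period before the end of the 5-day ambulatory pump use". They run by stage:

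- **Placement.** Among other reasons, subjects are discontinued if "blood is present in the catheter during insertion indicating possible vascular injury". Section 6, on catheter entry into the artery, says only that "the catheter will be withdrawn and the subject will not receive a pump".
- **Surgery.** Subjects are discontinued for signs of local anesthetic systemic toxicity (LAST) "or the catheter is inadvertently removed during the operation".
- **PACU.** "Subject will be removed if there are one or more signs of LAST (listed above) or if the catheter is removed inadvertently".
- **After discharge.** The wording changes. Subjects stop the pump, and "Subjects who must remove the pump early for any reason will be retained in the study for purposes of answering the pain surveys".

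On timing, section 6 says the pump is "attached to the catheter at the time the block is placed", and "Infusion will begin immediately after the surgery, when the patient is in the PACU".

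Protocol section 12 and SAP D1 analyse patients who are obliged to end pump use before 5 days, or choose to, both by intent-to-treat and per-protocol. Neither says which is primary. The only randomised subjects these sections treat as screening failures are those with a failed initial block and those withdrawn between randomisation and the block. Section 14 removes failed blocks from the control arm too, and gives prevention of bias as one reason.

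**The concern.** Two separate things look wrong.

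First, blood in the catheter and accidental catheter loss can occur only in the pump arm. If they take a subject out of the study, the groups compared at 12 months are no longer the groups that were randomised, and the loss is all on one side. The protocol took care to avoid this for failed blocks but not for catheter events.

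Second, once infusion is running in the PACU, the same subject is removed from the study under section 10 but belongs to an intent-to-treat analysis under section 12 and SAP D1. Two analysts could build different intent-to-treat sets from the same text. If section 10 is followed, the 12-month score may never be collected, and analysis cannot repair that later. Section 12 also says the pilot should inform a full study about drop-outs and incomplete treatments. These subjects are incomplete treatments, and their outcomes would be missing.

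**Working it through.** **Step 1. The texts side by side.**

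| Event before PACU discharge | Who can have it | Section 10 | Section 12 / SAP D1 | Result |
|---|---|---|---|---|
| Blood in catheter at insertion | Pump arm only | Discontinued | No rule names it | One-sided exclusion, no contradiction |
| Catheter loss in surgery | Pump arm only | Discontinued | Unclear: pump attached, not infusing | One-sided exclusion, no clear contradiction |
| Catheter loss in PACU, infusion started | Pump arm only | Removed | Natural reading: both analyses | One-sided, and a conflict on that reading |
| LAST in PACU, infusion started, pump subject | LAST is possible in either arm | Removed | Both analyses | Conflict, but not one-sided in itself |

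A catheter lost in the PACU before infusion starts belongs with the second row. Poor ultrasound view and persisting paresthesia, also listed in section 10, can arise from the single-shot block in either arm and are not part of the one-sided argument.

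**Step 2. The plan's own figure.** Section 12 gives power 0.8 for a 9-point SEFAS difference with 20 per group and alpha 0.05. It prints no SD, so the figure cannot be reproduced. Solving a two-sided two-sample t-test for power 0.80 at n = 20 per group gives d = 0.909, so SD = 9 / 0.909 = 9.90. Other conventions give 9.66 (Mann-Whitney efficiency 0.955, two-sided) to 11.45 (normal, one-sided). The textual point does not depend on this.

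**Step 3. How often.** The documents give no rate of catheter loss. The 0.4% blood aspiration rate in section 10 pools single and continuous blocks; taken at face value, the chance of at least one event in 20 is 1 − 0.996^20 = 0.08. At assumed rates of 5% and 10%, the expected number is 1 and 2 of 20, and the chance of at least one is 1 − 0.95^20 = 0.64 and 1 − 0.90^20 = 0.88. I use k = 1 and k = 2, all catheter events pooled.

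**Step 4. Bias with no treatment effect.** If the k removed subjects would have scored D points worse than the rest, the pump mean rises by (k/20) × D. D = 5 to 9 is assumed; 9 is the whole target effect. A negative D means they would have scored better. Rejection rates come from simulating the exact Mann-Whitney test with normal scores, SD 9.9, pump arm 20 − k, and a control arm of 20 that includes k comparable subjects (200,000 runs per cell, simulation error about 0.05 percentage points).

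| k | D | Bias (SEFAS points) | Pump-favouring rejections |
|---|---|---|---|
| 0 | – | 0 | 2.45% |
| 1 | 0 | 0 | 2.35% |
| 1 | 5 | +0.25 | 2.71% |
| 1 | 9 | +0.45 | 3.03% |
| 2 | 0 | 0 | 2.38% |
| 2 | 5 | +0.50 | 3.21% |
| 2 | 9 | +0.90 | 3.86% |
| 1 | −5 | −0.25 | 1.94% |
| 1 | −9 | −0.45 | 1.60% |
| 2 | −5 | −0.50 | 1.63% |
| 2 | −9 | −0.90 | 1.11% |

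The largest bias is 0.90 / 9.9 = 0.09 SD. Total two-sided rejection is 4.88% with no removals and 4.57% to 5.07% in the other cells.

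**Step 5. Power if these subjects are kept.** Suppose a delivered pump is worth 9 points and the affected subjects gain nothing. The effect of assignment is then 9 × (1 − 1/20) = 8.55 or 9 × (1 − 2/20) = 8.10.

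| k | Mann-Whitney power, excluded | Mann-Whitney power, kept |
|---|---|---|
| 0 | 0.78 | 0.78 |
| 1 | 0.76 | 0.73 |
| 2 | 0.75 | 0.68 |

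The excluded column assumes that removed subjects are not replaced from the enrolment allowance of 60.

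**The case against.** The strongest reply is that the conflict depends on a reading. An accidental catheter loss is arguably neither a required nor a chosen pump removal, so section 12 and SAP D1 may not reach it. That is fair, but then no analysis rule covers a randomised subject, and the text still needs repair. LAST in the PACU after infusion has begun does not have this difficulty: ending pump use there is plainly required.

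A second reply is that the retention sentence already settles the matter because it covers any reason. It stands in the after-discharge paragraph and may apply only there. If it does reach back to the PACU, section 10 contradicts itself.

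A third is that removal might mean removal from the pump only. The heading speaks of the study, and the after-discharge paragraph uses different terms for stopping the pump and staying in the study.

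A fourth is that enrolment of up to 60 for 40 evaluable subjects may allow replacement. That could restore numbers, but it would not restore the randomised comparison.

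Three stronger conclusions are tempting and not supported:

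- A reader might infer that every catheter event contradicts the intent-to-treat text. Blood at insertion and loss during surgery precede any infusion, so they do not clearly do so.
- A reader might infer that the analysis sections put these subjects in the primary dataset. They promise an intent-to-treat and a per-protocol analysis without naming either as primary.
- A reader might infer material bias in the trial result. No rate in the documents supports that, and the assumed cases show little effect.

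**Conclusion.** The point holds and is minor. Section 10 creates an exclusion after randomisation that only the pump arm can suffer. For pump subjects in the PACU with infusion running, it also conflicts with section 12 and SAP D1: clearly for LAST, and on the natural reading for accidental catheter loss.

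The likely numerical effect is small: at most 0.9 SEFAS points (0.09 SD), in a direction nobody can know in advance, with two-sided error near 5%. This rests on assumptions that the documents do not supply: 1 to 2 removals in 20, score differences of 5 to 9 points, normal scores, and an SD of 9.90 inferred from the stated power. If the removed subjects would have scored like the rest, there is no bias. The reason to act is that follow-up and analysis-set membership are unsettled for some randomised subjects, and that uncollected surveys cannot be recovered.

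**What to change.** Leave every clinical rule for stopping the pump as it is, and make two wording changes.

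1. In Protocol section 10, reconciled with section 12 and SAP D1, separate stopping the pump from leaving the study. Subjects with any listed event other than a failed single-shot block still receive all four SEFAS surveys unless they withdraw consent.
2. In SAP D1, state that the primary 12-month analysis is by randomised arm and includes these subjects, that failed blocks are excluded in both arms, and that per-protocol is a sensitivity analysis.

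Reporting catheter events and failed blocks by arm would be a useful but optional addition.

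The cost is document wording, a few extra surveys by web, mail or telephone, and some dilution. In the assumed cases, keeping these subjects instead of excluding them lowers Mann-Whitney power by 0.76 − 0.73 = 0.03 with one such subject and 0.75 − 0.68 = 0.07 with two. In return, the comparison stays between the randomised arms, apart from an exclusion that applies equally to both.
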